3.3.1 Baseline/Enrollment

The following data are planned to be collected at baseline for all enrolled participants:

- Demographics

- geography (zip code/ postcode)
 - age (date of birth)
 - gender
 - race/racial designation
 - ethnicity
 - education
- Medical History and Other Risk Factors
 - weight
 - height
 - baseline medical history including:
 - comorbidities that are thought to be potential risk factors including cardiovascular disease, lung disease, diabetes, kidney, blood disorders, and auto-immune conditions
 - history of depression, anxiety, and insomnia
 - prescription medications
 - frequency of use of certain medications of interest, including daily aspirin, Pepcid (famotidine), Tagamet HB (cimetidine), and antihistamine (cetirizine, loratadine)
 - use of supplements (vitamin D, zinc, other vitamins/minerals, herbals)
 - current smoking status
 - history of organ transplant
 - current treatment for cancer
 - pregnant
 - vaccinations, including childhood vaccinations (e.g. MMR) and seasonal flu
 - occupation, including healthcare worker or other job with heightened risk of exposure (e.g., grocery, daycare, mail/delivery)

- COVID-19
- type of test, test results and date of test, if any
- presence and severity (4-point scale) of symptoms including fever, cough, fatigue, dizziness, eye pain, blurry vision, shortness of breath, persistent pain or pressure in the chest, heart palpitations, new onset of confusion, inability to arouse, aches and pains, muscle twitching, rash, nasal congestion, runny nose,

sore throat, decreased sense of taste, decreased appetite, decreased sense of smell, diarrhea, vomiting, nausea, depression, anxiety, insomnia, other

- healthcare encounters, including type (telemedicine, office visit, emergency department, hospitalization), date, and whether the encounter was related to COVID-19
 - if hospitalized, duration of hospitalization
- household member has COVID-19 or flu-like symptoms
- receipt of COVID-19 vaccination, either as part of a clinical trial or standard of care once authorized by FDA or Medicines and Healthcare products Regulatory Agency (MHRA), along with date, manufacturer, and lot number if known, and whether it was the first shot or a booster shot.
 - among vaccinated:
 - symptoms following the vaccination including pain at injection site, swollen lymph nodes, fever, fatigue, headache, joint or muscle pain, nausea or vomiting, severe allergic reaction
 - impact symptoms had on ability to take care of yourself and ability to work
 - healthcare encounters, including hospitalization, following the vaccination
- medications including prescriptions (antimalarials, antivirals, antibiotics, biologics, corticosteroids, monoclonal antibody), over-the-counter (acetaminophen, nonsteroidal anti-inflammatory drugs [NSAIDs]),
 - for treatments the participant reports taking, timing of treatment relative to symptom onset
- participation in clinical trials or receipt of experimental treatments

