3.2.1 Inclusion Criteria

The following criteria must be met in order to be enrolled in the study:

- Adult (18 years or older)
- Currently living in the US or UK
- Have COVID-19 or COVID-19 like symptoms
- Received a COVID-19 vaccine
- Potential exposure to COVID-19

- Have regular access to a computer, smartphone or tablet and sufficient internet to support registry demands (note: this registry is designed to operate well even in regions with low bandwidth)
- Willing and able to provide informed consent
- Willing and able to follow the procedures of the study

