3.3 Data Sources and Collection

This is a direct-to-participant registry. All data will be reported by participants through a web-enabled application. No visits or examinations, laboratory tests or procedures are mandated or required for this study. Table 1 outlines reminders for participants to complete surveys, noting the technology will allow for participants to enter data at any time during the follow-up window.

Table 1. Data Collection Schedule

	Enrollment /Baseline	Month 1 (once a week)	Month 2 through 12 (twice a month)
Informed Consent	X		
Demography	X		
Static Medical History and Risk Factors (e.g., height, weight, occupation)	X		
Medical History (e.g., diagnoses, concomitant medications, vitamins/supplements, pregnancy, seasonal flu vaccine)*	X	X*	X*
COVID-19 test, if conducted	X	X	X
COVID-19 vaccination including manufacturer, date, lot number and first shot or booster, post-vaccine symptoms, and healthcare encounters for possible reactions, if available	X	X**	X**
COVID-19 symptoms	X	X	X
COVID-19 medications, both prescription and OTC, that may be intended as prophylactic or curative treatments	X	X	X

*Participants will be asked during follow-up if they had any changes in their underlying medical history (e.g., new diagnoses, new medications). If yes, they will report changes in key medical history that may influence COVID-19 risk factors and/or recovery (e.g., new comorbidities, pregnancy, etc).

**Participants reporting COVID-19 vaccination (first or second dose) will be moved into weekly follow-up, if not already in weekly follow-up, for 4 weeks after vaccination to capture subsequent symptoms and healthcare encounters as well as a second vaccine dose if applicable.

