 - comorbidities that are thought to be potential risk factors including cardiovascular disease, lung disease, diabetes, kidney, blood disorders, and auto-immune conditions
 - history of depression, anxiety, and insomnia
 - prescription medications

- frequency of use of certain medications of interest, including daily aspirin, Pepcid (famotidine), Tagamet HB (cimetidine), and antihistamine (cetirizine, loratadine)
- use of supplements (vitamin D, zinc, other vitamins/minerals, herbals)
- history of organ transplant
- current treatment for cancer
- pregnant
- flu vaccine

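### Baseline conditions carry no stated diagnosis date or order, so those first diagnosed after COVID-19 or a vaccine dose but before enrolment cannot be separated from pre-existing ones

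*Protocol*

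**What the plan says.** Protocol Section 3.3.1 lists, under a heading that covers medical history and other risk factors, "comorbidities that are thought to be potential risk factors including cardiovascular disease, lung disease, diabetes, kidney, blood disorders, and auto-immune conditions". It also lists "history of depression, anxiety, and insomnia", an item that Section 3.3.2 repeats for follow-up. Neither baseline item comes with a diagnosis date or a question on whether the condition came before or after COVID-19 or vaccination.

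Other items in Section 3.3.1 do carry a date or an order:
- Tests: "type of test, test results and date of test, if any".
- Vaccination: "along with date, manufacturer, and lot number if known, and whether it was the first shot or a booster shot".
- Encounters: "healthcare encounters, including type (telemedicine, office visit, emergency department, hospitalization), date, and whether the encounter was related to COVID-19".
- COVID-19 treatments: "timing of treatment relative to symptom onset".

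The inclusion criteria (Section 3.2.1) include "Have COVID-19 or COVID-19 like symptoms" and receipt of a COVID-19 vaccine, with no limit on the time since illness or dose. The synopsis presents these as alternative routes into the study. Objective 1 (Section 2) examines the role of underlying health conditions in the occurrence or severity of infection. Section 4.2.1 leaves in-depth analyses to later objective-specific plans.

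During follow-up, participants report changes in medical history since the previous survey. The footnote to Table 1 says that, if there were changes, "they will report changes in key medical history that may influence COVID-19 risk factors and/or recovery".

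**The concern.** In this registry, baseline is the date of joining and need not precede the infection or dose under study. For anyone who enrols after the event, a lung, blood or mood diagnosis made in between is reported in the same field, and in the same form, as one held for years.

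Two things follow. First, such a diagnosis can enter an Objective 1 analysis as an underlying condition although it came after the infection. If it is more common in cases than in non-cases, or in severe than in mild illness, it creates or enlarges an association. Second, the same diagnosis cannot later be identified as having arisen after the event.

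A later analysis plan cannot repair this, because the information would never have been collected. Section 3.3 requires no examinations or laboratory tests, and Section 5.1 says there are no source documents, so the protocol provides no second record to consult.

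**Working it through.** The protocol gives no figure on this point, so there is nothing to reproduce. The check has two parts.

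**1. Which items can be placed in time**

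| Item | Baseline (3.3.1) | Follow-up (3.3.2) |
|---|---|---|
| Test | date | date |
| Vaccination | date, and first or booster | date |
| Healthcare encounter | date, and relation to COVID-19 | date, and relation to COVID-19 |
| COVID-19 treatment | timing relative to symptom onset | timing relative to symptom onset |
| Comorbidity; depression, anxiety, insomnia | none stated | change since the previous survey |

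The gap is at baseline. In follow-up, a new diagnosis falls between two completed surveys: 7 days apart when weekly, about 15 days when twice a month (365.25/12/2 = 15.2), or about 30 days under the monthly schedule in the synopsis. A missed survey widens the interval but does not remove it.

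**2. How large the bias could be (all inputs assumed, none from the protocol)**

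- p0: prior prevalence of the condition, equal in cases and non-cases, so the true odds ratio is 1.
- i: share of cases without the condition who are first diagnosed between infection and enrolment.
- b: the same share in non-cases over a comparable window.

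Reported prevalence is p1 = p0 + (1 − p0)·i in cases and p2 = p0 + (1 − p0)·b in non-cases. The apparent odds ratio is [p1/(1 − p1)] / [p2/(1 − p2)]. The share of the conditions reported by cases that arose after infection is (p1 − p0)/p1.

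With p0 = 10% and b = 0:
- i = 1%: p1 = 0.10 + 0.90 × 0.01 = 0.109. OR = (0.109/0.891)/(0.10/0.90) = 1.10. Share after infection = 0.009/0.109 = 8%.
- i = 5%: p1 = 0.10 + 0.90 × 0.05 = 0.145. OR = (0.145/0.855)/(0.10/0.90) = 1.53. Share after infection = 0.045/0.145 = 31%.

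Apparent odds ratio over a wider range, with b = 0:

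| p0 | i = 0.5% | i = 1% | i = 3% | i = 5% |
|---|---|---|---|---|
| 5% | 1.10 | 1.20 | 1.62 | 2.05 |
| 10% | 1.05 | 1.10 | 1.31 | 1.53 |
| 20% | 1.03 | 1.05 | 1.15 | 1.26 |

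Sensitivity to b:
- With b = 0.5% the whole grid runs from 1.00 to 1.87.
- With i = b the ratio is exactly 1.00.
- If non-cases gain more diagnoses than cases, the ratio falls below 1. For p0 = 10%, i = 0.5%, b = 1%: (0.1045/0.8955)/(0.109/0.891) = 0.95.
- Steeper inputs give more. With p0 = 20%, i = 8%, b = 1%: p1 = 0.264, p2 = 0.208, OR = 1.37.

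With diagnoses placed in time, those made after infection can be left out of the exposure, and the ratio in this illustration returns to 1.00.

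**The case against.** The strongest reply is that Section 3.3.1 is a list of planned topics. The questionnaire is not shown and may ask for dates, and Section 5.3 expects the instrument to be refined. This makes the gap an inference, but a reasonable one, because the same list names dates or timing for four other kinds of item and not for this one.

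A second reply is that many participants may join while acutely ill, which leaves little time for a new chronic diagnosis. For them the bias is small, as the low-incidence columns show. But the protocol sets no limit on time since illness or dose, and the baseline survey itself asks about past tests, hospital stays and post-vaccine symptoms.

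Third, other items give partial help. Depression, anxiety and insomnia are also rated as COVID-19 symptoms on a 4-point scale, and encounters are dated. Neither dates a reported diagnosis, and no link between an encounter and a diagnosis is described.

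Three stronger readings are tempting, and the protocol does not support them:
- *That diagnoses made during follow-up also lack any order.* They are reported as changes since the previous survey, so they can be placed against dated tests and doses within the survey gap.
- *That the plan treats later conditions as causes.* No such analysis rule is fixed. A heading in a data list does not assign an analytic role, and Section 4.2.1 defers the analyses.
- *That new diagnoses are main outcomes for long COVID or vaccine safety.* Objective 2 names post-vaccine symptoms and COVID-19 infection, and Section 3.1 speaks of longer-term progression, treatment and lingering or worsening symptoms.

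**Conclusion.** The point holds for the baseline survey. As listed, the data cannot separate a condition that preceded COVID-19 or vaccination from one first diagnosed between that event and enrolment. The first consequence is a possibility that depends on the later analysis: such a condition can be counted as an underlying condition. The second does not depend on it: the condition cannot be identified afterwards as a post-event diagnosis.

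The size is uncertain. The figure of about 1.10 to 1.53 rests on 10% prior prevalence, 1% to 5% of previously unaffected cases newly diagnosed before enrolment, none in non-cases, and no true effect. At 0.5% it is 1.05, and with equal rates in both groups there is no bias. The direction is not guaranteed either. The change is worth making because it is cheap and the loss cannot be repaired at the analysis stage.

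**What to change.** In Section 3.3.1, for each reported comorbidity and for history of depression, anxiety and insomnia, add the month and year of first diagnosis. A shorter alternative is to ask whether it was first diagnosed before or after the first COVID-19 symptoms or positive test and, if vaccinated, before or after the first dose. Analyses of underlying conditions can then be restricted to those that came before the event.

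Optionally, add the same date to the change question in Section 3.3.2. This is a refinement, because order there is already bounded by the last completed survey.

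The cost is one short extra question per reported condition, or two for vaccinated participants if the before/after form is used, and some recall error in dates. Participants who report no condition are not affected.

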Original	March 27, 2020	N/A
V2.0	April 13, 2020	Revised study title and added 3 months of longitudinal follow-up
V3.0	December 7, 2020	Revised duration of follow-up from 3 months to 12 months, removed questions on social distancing, and added questions on mental health conditions, healthcare encounters, and vaccines.
V4.0	March 9, 2021	Revised inclusion criteria to include vaccinated adults as well as participants from the UK; added questions about post-vaccination symptoms and health care encounters.

List of Abbreviations

COVID-19	coronavirus disease 2019
FDA	U.S. Food and Drug Administration
GDPR	General Data Protection Regulation
GPP	good pharmacoepidemiology practices
HIPAA	Health Insurance Portability and Accountability Act of 1996
ICF	informed consent form
ICH	International Council for Harmonisation of Technical Requirements for Pharmaceuticals for Human Use
IEC	independent ethics committee
IRB	institutional review board
ISPE	International Society for Pharmacoepidemiology
NSAID	nonsteroidal anti-inflammatory drugs

Study Synopsis

Full Study Title: Registry to study factors that may impact COVID-19 occurrence and severity

Background & Rationale: The 2019 coronavirus disease (COVID-19) has presented major challenges to countries around the world. Currently there is little information about (1) symptom presentation, severity, and duration especially for cases that do not require hospitalization, (2) understanding which prescription medications, if any, influence risk, including various hypertension and anti-diabetic medications, (3) whether vitamin and mineral supplements, alone or in combination with established medications offer any degree of protection, and (4) what medical management is most effective at reducing the high toll of this infection.

Initial research suggests a wide range of potential symptoms including those that would be expected with a respiratory virus (e.g., fever, cough) as well as gastrointestinal issues, dizziness, inability to concentrate, and effects on the sense of smell and taste. Additionally, there are a wide range of treatments, both prescribed and over-the-counter, that are being used to manage symptoms. Systematic data collection and analytics will contribute empirical information about benefits and risks that could have immediate public health impact. This registry will enroll participants in an observational, direct-to-participant longitudinal study to assess disease risk, progression, treatments, and vaccines.

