2. OBJECTIVES

The objectives of this study are to:

1. Identify factors that may impact the occurrence or severity of COVID-19 infections including examining the role of underlying health conditions, prescription and over-the-counter medications, vitamins and supplements.
2. Assess post-vaccine symptoms and COVID-19 infection among participants reporting a COVID-19 vaccination

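### The medical-history items do not ensure capture of why people take the acid reducers and antihistamines under study, so confounding by indication may not be controllable

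*Protocol*

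**What the plan says.** Objective 1 (section 2) makes associations between medicines and outcomes an aim of the study: "examining the role of underlying health conditions, prescription and over-the-counter medications, vitamins and supplements".

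Section 3.3.1 names particular exposures and asks about "frequency of use of certain medications of interest, including daily aspirin, Pepcid (famotidine), Tagamet HB (cimetidine), and antihistamine (cetirizine, loratadine"). Section 3.3.2 repeats this at follow-up for participants who report a change in medical history.

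The conditions to be recorded are, in both sections, "comorbidities that are thought to be potential risk factors including cardiovascular disease, lung disease, diabetes, kidney, blood disorders, and auto-immune conditions". Depression, anxiety, insomnia, organ transplant, current cancer treatment and pregnancy are listed separately. Reflux, heartburn and allergy do not appear as medical-history items.

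No medicine has a reason-for-use item. The nearest detail concerns COVID-19 treatments only: "for treatments the participant reports taking, timing of treatment relative to symptom onset".

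Table 1 (section 3.3) has a more general row: "Medical History (e.g., diagnoses, concomitant medications, vitamins/supplements, pregnancy, seasonal flu vaccine"). Its footnote narrows follow-up updates to history that may bear on COVID-19 risk or recovery.

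The COVID-19 symptom list includes "aches and pains, muscle twitching, rash, nasal congestion, runny nose", followed by sore throat.

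**The concern.** People take acid reducers and antihistamines for a reason, and that reason is the first way in which users differ from non-users. If the reason is also related to the outcome as recorded, the medicine will appear associated with the outcome even when it does nothing. To deal with this, an analyst needs to know who has the condition, in order to adjust for it or to compare users and non-users among people who have it.

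Allergy is the sharpest case because the protocol itself supplies the link to the outcome. Allergic rhinitis commonly produces a runny nose, congestion and a sore throat, and all three are recorded as COVID-19 symptoms. Antihistamine use could then track COVID-like illness with no drug effect at all.

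The choice of analysis method can wait for the objective-specific analytic plans mentioned in section 4.2.1. The choice of what to ask cannot, since no later plan can recover a variable that was never collected. Section 3.2 allows for millions of respondents, but a large sample reduces random error and leaves this bias unchanged.

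**Working it through.** The protocol states no effect size, power or bias figure, so there is nothing to reproduce. The check has two parts.

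**1. Named exposures set against named conditions (sections 3.3.1 and 3.3.2)**

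| Medication of interest | Usual reason for use | Named condition that matches |
|---|---|---|
| Daily aspirin | Cardiovascular disease | Cardiovascular disease |
| Famotidine, cimetidine | Reflux, heartburn | None |
| Cetirizine, loratadine | Allergic rhinitis, seasonal allergy | None |

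Two of the three groups have no matching condition, and no reason-for-use item fills the gap.

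**2. How large the bias could be (illustration only)**

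Let U be the unrecorded indication, p1 and p0 its prevalence in users and non-users, and g the ratio by which U raises the recorded outcome. With a true medicine effect of RR = 1,

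apparent RR = [1 + p1(g − 1)] / [1 + p0(g − 1)].

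Every input below is an assumption; none comes from the protocol.

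Allergy and antihistamines, p1 = 0.80, p0 = 0.15:
- g = 1.0: 1.00 / 1.00 = 1.00
- g = 1.2: 1.16 / 1.03 = 1.13
- g = 1.5: 1.40 / 1.075 = 1.30
- g = 2.0: 1.80 / 1.15 = 1.57

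Sensitivity to the assumed prevalences:

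| p1 / p0 | g = 1.0 | g = 1.2 | g = 1.5 | g = 2.0 |
|---|---|---|---|---|
| 0.5 / 0.1 | 1.00 | 1.10/1.02 = 1.08 | 1.25/1.05 = 1.19 | 1.50/1.10 = 1.36 |
| 0.7 / 0.15 | 1.00 | 1.14/1.03 = 1.11 | 1.35/1.075 = 1.26 | 1.70/1.15 = 1.48 |
| 0.9 / 0.2 | 1.00 | 1.18/1.04 = 1.13 | 1.45/1.10 = 1.32 | 1.90/1.20 = 1.58 |

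For g between 1.2 and 2.0 the apparent RR is about 1.1 to 1.6.

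Reflux and acid reducers, p1 = 0.90, p0 = 0.15: 1.09/1.015 = 1.07 at g = 1.1, and 1.45/1.075 = 1.35 at g = 1.5. Here nothing in the protocol ties the indication to the outcome, so g = 1.0 and no bias is just as open.

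The same factor can hide a benefit. At a bias factor of 1.30, and assuming it multiplies the true effect, a true RR of 1/1.30 = 0.77 would be observed as 1.0.

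**The case against.** The strongest reply is that the protocol does not close the door. The comorbidity list is introduced as examples, Table 1 collects diagnoses in general terms, and the questionnaire is not shown, so it may contain an allergy, reflux or other-condition box. Section 5.3 also allows the instrument to be refined. A reader might infer that the confounding can never be removed; for these reasons the documents do not support that. The reply does not settle the matter, however. The lists are open only to further potential risk factors, the Table 1 footnote restricts updates in the same way, and section 5.3 plans to keep free text to a minimum. A questionnaire written from this text would probably leave both indications out.

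A second reply is that selecting on outcome risk is sound, because a condition unrelated to the outcome cannot confound; the g = 1.0 column shows this. That stands. A reader might infer that the selection rule is itself wrong, but the fault is only that it stops there.

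Third, a reader might add hypertension to the gaps, because the synopsis asks about "understanding which prescription medications, if any, influence risk, including various hypertension and anti-diabetic medications". That is not supported as an omission. Cardiovascular disease may well include hypertension, and antihypertensives are not among the named medications of interest. At most, the category is broad.

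Fourth, other routes exist. Test results and hospitalization are recorded, individual symptoms can be left out of an outcome, and two medicines are named in each class. This reduces the problem without removing it. Tests are not mandated (section 3.3), and section 1 describes a need for data from people who may lack access to one, so symptom-based outcomes will matter. Comparing cetirizine with loratadine, or famotidine with cimetidine, balances the indication but cannot show whether using the class at all changes risk.

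**Conclusion.** The point holds in a limited form. For acid reducers and antihistamines, sections 3.3.1 and 3.3.2 neither name the usual indication nor list a reason for use. The protocol therefore does not ensure that confounding by indication can be controlled in user versus non-user comparisons.

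The weight falls mainly on antihistamines with symptom-based outcomes, where the protocol's own symptom list makes the link. It is less for test-confirmed infection or hospitalization, and for acid reducers it depends on a relation between reflux and the outcome for which the protocol offers no evidence either way.

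The risk ratios of about 1.1 to 1.6 show what a moderate relation would do. They are not estimates for this registry. They rest on assumed prevalences, on an assumed 1.2 to 2.0 fold rise in reported COVID-like illness with allergy, and on neither the condition nor a reason for use being captured by a questionnaire that is not shown. How comparisons are adjusted belongs to the analytic plans and is not part of this point.

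**What to change.** In sections 3.3.1 and 3.3.2, widen the comorbidity item to conditions that are potential risk factors or indications for the medications of interest. Then do one of the following:

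- add check boxes for reflux/heartburn and for allergic rhinitis/seasonal allergy; or
- add a reason-for-use question for each medication of interest.

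Optionally, record hypertension separately within cardiovascular disease, since the synopsis raises hypertension medicines as a question.

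The cost is a few seconds of participant time at baseline and at medical-history updates. The version history shows that questions were added in V3.0 and V4.0, so the route exists. People already enrolled need to be asked at their next survey whether or not they report a change in medical history; otherwise they will lack the item, as will anyone who has already finished follow-up.

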1. BACKGROUND AND RATIONALE

The ongoing coronavirus disease (COVID-19) pandemic has caused a worldwide crisis in terms of social, medical and financial systems. The number of cases globally has increased significantly since the first reported case in December 2019. Initially, the disease was thought to severely affect primarily older patients (60 years and above)¹ but as the virus continues to spread, it has become evident that several other patient populations are at high risk for hospitalization, complications, and even death².

The United States has been severely burdened by COVID-19, with over 28 million cases and 500,000 deaths reported as of 25 February 2021³. Additionally, there have been evolving reports of COVID-19 symptoms and progression^{4,5,6,7}, making it difficult for people to determine when they should seek medical attention and/or quarantine for suspected COVID-19 illness. Therefore, there is a need for systematic data collection from people who may be infected with COVID-19 but may not have access to a test to confirm their diagnosis.

Currently, there is a paucity of data describing disease risk, symptoms, and non-prescription medication use including supplements among the broader non-hospitalized community. Most publicly available data is limited to surveillance of the number of tested cases and the number of deaths, with little to no longitudinal follow-up of symptom progression, outcomes, treatments, and other related information. In addition, there is a need for long-term follow-up for people receiving COVID-19 vaccinations to continue to monitor safety and effectiveness outside of well controlled clinical trials and as COVID-19 strains evolve over time.

With recent Emergency Use Authorization of several COVID-19 vaccines, there is also a need to understand broad and long-term safety and effectiveness of the COVID-19 vaccines over time and as new strains emerge.

Systematic data collection and analytics would contribute empirical information about benefits and risks that could have immediate public health impact. This Registry will enroll participants in an observational, direct-to-participant longitudinal study to assess disease risk, progression, treatments, and vaccines.

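### Baseline has no direct question on earlier COVID-19 and no onset date or recall window for symptoms, so a past illness without test, care or treatment cannot be told from no infection

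*Protocol*

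**What the plan says.** Section 2 of the protocol sets two objectives that concern infection. Objective 1 is to "Identify factors that may impact the occurrence or severity of COVID-19 infections"; Objective 2 is to "Assess post-vaccine symptoms and COVID-19 infection among participants reporting a COVID-19 vaccination". Section 1 gives as one reason for the registry the need for data from "people who may be infected with COVID-19 but may not have access to a test to confirm their diagnosis".

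Section 3.3.1 lists the baseline data. The COVID-19 items that could bear on an earlier illness are:

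- tests: "type of test, test results and date of test, if any";
- symptoms: "presence and severity (4-point scale) of symptoms including fever, cough, fatigue" and others, with neither an onset date nor a period to which the answer refers;
- healthcare encounters, with type, "date, and whether the encounter was related to COVID-19", and "if hospitalized, duration of hospitalization";
- COVID-19 medications, and "for treatments the participant reports taking, timing of treatment relative to symptom onset".

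Previous COVID-19 is not among the named comorbidities. Table 1 in Section 3.3 has a medical history row that mentions diagnoses in general. The study population paragraph of the Synopsis lets an adult enter on vaccination or exposure alone, and Section 3.2.2 does not exclude people who have already had COVID-19.

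**The concern.** To study who becomes infected, or who becomes infected after vaccination, one must be able to separate new infections from old ones and people still susceptible from people already infected. Version 4.0 (March 2021) admitted vaccinated adults at a time when Section 1 already cites over 28 million reported US cases. Some entrants will therefore have had COVID-19 and recovered, and some of those will never have been tested.

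If earlier infection gives some protection and goes unrecorded, infection rates after enrolment are lower than in truly susceptible people. If it is also unevenly spread across the groups compared, for example by occupation or household exposure, the risk-factor estimates are distorted as well. The choice of analysis set can be left to a later plan, but the variable needed to make that choice has to be collected.

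**Working it through.** **Step 1: what each baseline item can identify.** Take a participant who had COVID-19 some months before enrolment and has recovered.

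- Tested: the dated test result shows it.
- Untested, but sought care: the encounter item shows it, because it is dated and flagged as COVID-19-related. It covers telemedicine and office visits as well as emergency department visits and hospital stays.
- Untested, no care, but treated: the medication item and treatment timing may show it. The timing is relative to symptom onset, and no onset date is listed, so the illness may not be placed in calendar time.
- Told of a diagnosis: the general diagnoses entry in Table 1 might show it, but COVID-19 is not named there.
- Untested, no care, no treatment: only the symptom item remains. Without a recall window, a participant who is now well may reasonably report no symptoms. A participant who does report past symptoms gives no date.

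The last row is the gap. It falls within the group that Section 1 says the registry needs to reach.

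**Step 2: size.** The protocol states no sample size, effect size, infection rate or level of protection, so there is no figure of its own to reproduce. Everything below is an assumption for scale.

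Let q be the share with unrecorded earlier infection among people treated as not previously infected, and e the relative protection from that infection.

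Observed incidence ÷ incidence in susceptible people = 1 − q·e

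| q | e = 0.5 | e = 0.8 | e = 0.9 |
|---|---|---|---|
| 5% | 0.975 | 0.960 | 0.955 |
| 10% | 0.950 | 0.920 | 0.910 |
| 20% | 0.900 | 0.840 | 0.820 |
| 30% | 0.850 | 0.760 | 0.730 |

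The range is 0.73 to 0.975.

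For a comparison of group 1 with group 0, observed risk ratio = true risk ratio × (1 − q₁·e) ÷ (1 − q₀·e).

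| q₁ vs q₀ | e = 0.5 | e = 0.8 | e = 0.9 |
|---|---|---|---|
| 10% vs 10% | 1.000 | 1.000 | 1.000 |
| 5% vs 20% | 1.083 | 1.143 | 1.165 |
| 20% vs 5% | 0.923 | 0.875 | 0.859 |
| 10% vs 30% | 1.118 | 1.211 | 1.247 |
| 30% vs 10% | 0.895 | 0.826 | 0.802 |

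The multiplier runs from about 0.80 to 1.25 and is exactly 1 when the shares are equal.

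**Step 3: an example.** With a true risk ratio of 2.0, 30% against 10% unrecorded and 80% protection, the observed ratio is 2.0 × 0.76 ÷ 0.92 = 1.65, so 35% of the excess risk is lost. With 50% protection it is 2.0 × 0.85 ÷ 0.95 = 1.79.

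**The case against.** Section 3.3.1 describes categories of data planned for collection, often with open lists, and the questionnaire itself is not shown. The actual symptom or diagnosis questions might ask about past illness. That is fair, but the protocol is where the data content is fixed, and as written it does not require such a question.

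The in-depth analyses are left by Section 4.2.1 to objective-specific plans, so the choice of analysis population is no fault of the protocol. This stands: the absence of a population definition is not part of the point. It does not dispose of the uncollected variable.

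The added question would not fully solve the problem. Self-reported suspected illness cannot be verified, and some people who answer yes will never have been infected. This also stands, and limits what the fix can achieve.

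A reader might infer more than the document supports, in four ways:

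- *That test results are the only baseline information on earlier COVID-19.* The encounter, hospitalization and treatment items, and possibly the diagnoses entry, identify some untested cases.
- *That recovered participants are placed in the at-risk group.* The protocol defines no such group, and occurrence need not be analysed as incidence among susceptible people.
- *That risk-factor estimates are pulled toward or past no effect.* The direction depends on which group has more unrecorded infection. Healthcare workers, for example, may have been tested more often and so have less of it. To cross the null from a true ratio of 2.0, with 80% protection and 10% unrecorded in the comparison group, needs 1 − 0.8·q₁ < 0.92 ÷ 2 = 0.46, that is q₁ above 67.5%.
- *That Version 4.0 opened entry to exposed adults.* The version history credits it with vaccinated adults and UK participants only.

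**Conclusion.** The point holds in a limited form. Baseline lacks a direct item on earlier COVID-19 and dates neither the onset nor the recall period of symptoms. Participants who recovered without a test, COVID-19-related care or treatment therefore cannot be reliably distinguished from those never infected. How many there will be cannot be told from the document.

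On the assumed ranges the effect on incidence is a reduction of 2.5% to 27%, and this needs no comparison group to arise, so it bears directly on the infection part of Objective 2. The effect on risk ratios may be nil or may go either way, up to roughly a fifth down or a quarter up. These figures rest on assumed shares and protection, and on the unrecorded cases being analysed as if never infected. The protocol does not prescribe that, but without the variable an analysis would have little means of avoiding it.

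**What to change.** Add to the COVID-19 block of Section 3.3.1 a question on COVID-19 before any current illness, with the answers test-confirmed, told by a clinician, suspected, or no, and the month and year. Put the same question to current participants at their next scheduled survey. State an onset date and a recall window for the baseline symptom item. The objective-specific analyses can then separate or stratify previously infected participants as their plans decide.

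Section 5.3 already foresees refinement of the data collection instrument, so the change fits the existing process. The cost is one more question and a small extension to another. Recall error and misclassification will remain for suspected illness, which is a reason to keep the answer categories apart in analysis. Earlier infection without symptoms will still be missed unless it was picked up by a test.
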